#### 7.2.3 Serious Adverse Events (SAEs)

All SAEs, regardless of attribution, occurring from time of signed informed consent, through 30 days after the last administration of study drug, must be reported upon discovery or occurrence.

An SAE is defined in regulatory terminology as any untoward medical occurrence that:

- **Results in death.**

If death results from (progression of) the disease, the disease should be reported as event (SAE) itself.

- **Is life-threatening.**

The patient was at risk of death at the time of the event; it does not refer to an event that hypothetically might have caused death if it were more severe.

- **Requires in-patient hospitalization or prolongation of existing hospitalization for  $\geq 24$  hours.**
- **Results in persistent or significant disability or incapacity.**
- **Is a congenital anomaly/birth defect.**
- **Is an important medical event.**

Any event that does not meet the above criteria, but that in the judgment of the investigator jeopardizes the patient, may be considered for reporting as a serious adverse event. The event may require medical or surgical intervention to prevent one of the outcomes listed in the definition of "Serious Adverse Event".

For example: allergic bronchospasm requiring intensive treatment in an emergency room or at home; convulsions that may not result in hospitalization; development of drug abuse or drug dependency.

#### 7.2.4 Unanticipated Problems Involving Risks to Subject or Others

A UPIRSO is a type of SAE that includes events that meet ALL of the following criteria:

- is unexpected (in terms of nature, severity, or frequency) given the procedures described in the research protocol documents (e.g., the IRB-approved research protocol and informed consent document) and the characteristics of the human subject population being studied
- is related or possibly related to participation in the research ("possibly related" means there is a reasonable possibility that the incident, experience, or outcome may have been caused by the procedures involved in the research); and
- suggests that the research places human subjects or others at a greater risk of harm (including physical, psychological, economic, or social harm) than was previously known or recognized, even if no harm has actually occurred.

### 7.3 Adverse Event Reporting

#### 7.3.1 Routine Reporting

All routine adverse events, such as those that are expected, or are unlikely or definitely not related to study participation, are to be reported on the appropriate eCRF. Routine AEs will be reviewed by the Data and Safety Monitoring Committee (DSMC) according to the study's phase and risk level, as outlined in the DSMP.

#### 7.3.2 Determining if Expedited Reporting is Required

This includes all events that occur within 30 days of the last dose of protocol treatment. Any event that occurs more than 30 days after the last dose of treatment and is attributed (possibly, probably, or definitely) to the agent(s) must also be reported accordingly.

- 1) Identify the type of adverse event using the NCI CTCAE v 5.0.
- 2) Grade the adverse event using the NCI CTCAE v 5.0.
- 3) Determine whether the adverse event is related to the protocol therapy. Attribution categories are as follows:
  - Definite: AE is clearly related to the study treatment.
  - Probable: AE is likely related to the study treatment.
  - Possible: AE may be related to the study treatment.
  - Unlikely: AE not likely to be related to the study treatment.
  - Unrelated: AE is clearly NOT related to the study treatment.
- 4) Determine the prior experience of the adverse event. Expected events are those that have been previously identified as resulting from administration of the agent. An adverse event is considered unexpected, for expedited reporting purposes only, when either the type of event or the severity of the event is not listed in:
  - the current protocol
  - the drug package insert
  - the current Investigator's Brochure

#### 7.3.3 Expedited Reporting of SAEs/Other Events

**7.3.3.1 Reporting to the Northwestern University QAM/DMC**

All SAEs must be reported to the assigned QAM within 24 hours of becoming aware of the event. Completion of the NU CTO SAE Form, provided as a separate document, is required.

The completed form should assess whether or not the event qualifies as a UPIRSO. The report should also include:

- Protocol description and number(s)
- The patient's identification number
- A description of the event, severity, treatment, and outcome (if known)
- Supportive laboratory results and diagnostics
- The hospital discharge summary (if available/applicable)
- Country of incidence

All SAEs will be reported to, and reviewed by, the DMC per the DSMP.

**7.3.3.2 Reporting to the Northwestern University IRB**

*The following information pertains to the responsibilities of the lead site (Northwestern University). Additional participating sites should follow their local IRB guidelines for reporting to their local IRBs.*

- Any death of an NU subject that is unanticipated in nature and at least possibly related to study participation will be promptly reported to the NU IRB within 24 hours of notification.
- Any death of a non-NU subject that is unanticipated and at least possibly related and any other UPIRSOs will be reported to Northwestern University and to the NU IRB within 5 working days of notification.
- Information pertaining to an NU subject that fits into any of the categories listed on the Reportable New Information page will be reported to the NU IRB within 5 business days of knowledge or notification

**7.3.3.3 Reporting to VasGene Therapeutics, Inc**

SAEs will be reported within 24 hours/1 business day to VasGene Therapeutics by e-mail ([[contact]](mailto:[contact])) using the NU CTO SAE form.

**7.3.3.4 Reporting to the FDA**

The FDA will be notified within 7 calendar days of any SAE that is associated with study treatment, is unexpected, and is fatal or life-threatening.

The FDA will be notified within 15 calendar days of any SAE that is associated with the study treatment, unexpected, and serious but not fatal or life-threatening. This includes any previous SAEs that were not initially deemed reportable, but are later determined to meet the criteria for reporting (i.e. by the DSMC).

All other SAEs will be reported on an annual basis as part of the annual FDA report.

**8 DRUG INFORMATION**

**8.1 sEphB4-HSA**

**8.1.1 Other names**

None

**8.1.2 Classification - type of agent**

sEphB4-HSA is a fully human recombinant protein consisting of the extracellular domain (aa 1 to 522) of EphB4 receptor at the N-terminus and human albumin (aa 1 to 585) at the C-terminus. sEphB4-HSA specifically binds to EphrinB2, a trans-membrane ligand and member of Ephrin ligand family. EphrinB2 is the only ligand for EphB4 receptor.

**8.1.3 Mode of action**

sEphB4-HSA binds to EphrinB2 with high affinity (5-10nM) and blocks interaction with cell surface EphB receptors, thus blocking forward and reverse signaling.

**8.1.4 Storage and stability**

The Drug Product contains sEphB4-HSA at 25 mg/mL in 10 mM L-Histidine, 150 mM Sodium Chloride, and 10% Sucrose, pH 7.0.

sEphB4-HSA vials must be stored at a temperature 2-8°C and should be protected from light. Recommended safety measures for preparation and handling of sEphB4-HSA using standard practice. Once diluted in an IV bag for administration, sEphB4-HSA can be stored for up to 12 hours at room temperature/under room light and 24 hours at 2° to 8°C in the refrigerator. Care must be taken to ensure sterility of the prepared solution as the product does not contain any antimicrobial preservative or bacteriostatic agent.

**8.1.5 Protocol dose specifics**

sEphB4-HSA will be given as 1000mg IV infusion over 60 minutes ( $\pm 15$  minutes) every 2 weeks on day 1 ( $\pm 3$ ) of each cycle during Cycles 1-6 (1 cycle =14 days). Beginning at Cycle 7, patients will receive sEphB4-HSA every 3 weeks on Day 1 of each cycle (1 cycle = 21 days).

Refer to Table 4-2-1 for required premedication regimens.

**8.1.6 Preparation**

- Each vial contains 250 mg of drug in a 10 mL volume (vial concentration 25 mg/mL).
- The product is a clear, colorless to light straw yellow sterile solution in 10 mL glass vials.
- Allow the appropriate number of vials of sEphB4-HSA to stand at room temperature for approximately 15 minutes before preparation.
- Ensure that the sEphB4-HSA solution is a colorless, clear to slightly opalescent solution, essentially free of particles on visual inspection.
- Aseptically withdraw the required volume of sEphB4-HSA solution into a syringe, and dispense into an IV bag. (If multiple vials are needed for a subject, it is important to use a separate sterile syringe and needle for each vial to prevent problems such as dulling of needle tip, stopper coring, repeated friction of plunger against syringe barrel wall and so on).
- The necessary dose should be diluted in appropriate size bag of 0.9% sodium chloride to a total volume of 200 mL. EVA, PVC-free or PVC bags can be used for drug preparation.
- Mix by GENTLY inverting several times. DO NOT shake.
- Visually inspect the final solution. If the infusion is not clear or the contents appear to contain precipitate, the solution should be discarded and documented on the Drug Accountability Log.
- Administer over 60 ( $\pm 15$ ) minutes via 0.2  $\mu$ m in-line filter.
- Care must be taken to ensure sterility of the prepared solution as the product does not contain any antimicrobial preservative or bacteriostatic agent.

**8.1.7 Route of administration for this study**

Administered IV via peripheral or central line. Administer with 0.2 µm in-line filter.

**8.1.8 Incompatibilities**

No known incompatibilities, sEphB4-HSA should be given through a dedicated intravenous line. Do not co-administer other medications at the same line.

**8.1.9 Availability & Supply**

sEphB4-HSA will be shipped to each site from VasGene Therapeutics, Inc. Additional supplies can be ordered using the drug supply form provided VasGene Therapeutics, Inc. The product is a clear, colorless to light straw yellow sterile solution in 10 ml glass vials. Each vial contains 250 mg of drug in a 10 mL volume (vial concentration 25 mg/ml). The vial is closed with an appropriately sized stopper and seal.

**8.1.10 Side effects**

Please refer to most recent for IB for full list of Reported Adverse Events.

**8.1.11 Nursing implications**

Attach the IV bag containing the sEphB4-HSA solution to administration set (tubing) with 0.2 µm in-line filter, and infusion pump. The infusion rate of the infusion pump should be adjusted to allow for a total infusion time of 60 minutes ( $\pm 15$  minutes). At the end of the infusion period, flush the line with a sufficient quantity of normal saline. Do not administer study drug as an i.v. push or bolus injection.

**8.1.12 Return and Retention of Study Drug**

Any partially used and unused drug can be destroyed per the institution's drug destruction policy

## 9 CORRELATIVES/SPECIAL STUDIES

Correlative Samples - Details for Lab Manual			
Correlative study	Recent archival tumor tissue (primary and metastatic) if available.	Blood	
Mandatory or Optional	Optional	Mandatory	
Timing (+/- windows)	When requested by the Principal Investigator or Principal Investigator's designee; Samples may be collected at any time during the study per PI request.	Baseline, cycle 5 day 1, EOT	
Volume Needed (blood only)	--	10ml	2ml
Tube type needed (blood only)	--	10ml EDTA tubes	Draw blood in a plain, red-top tube(s), serum gel tube is acceptable.
Tissue thickness and/or # slides (tissue only)	Up to 12 slides at 5µm thickness	--	
Processing center (e.g. PCF-CTU)	Each Institution	Each Institution	Spin down within 2 hours and send 1 mL of serum frozen in a plastic vial.
Sample handling/processing instructions	Each institution will send samples to NU PCF-CTU	Each institution will send samples to NU PCF-CTU	Each institution will send samples to NU PCF-CTU
Contact person	[contact]	[contact]	[contact]
Shipping/delivery info	PCF-CTU  Samples must be shipped overnight Monday-Thursday only .	PCF-CTU  Samples must be shipped overnight Monday-Thursday only .	PCF-CTU  Samples must be shipped overnight Monday-Thursday only .
Storage needs	For long term, sections will be stored at 4°C	For long term, samples will be stored at -80°C at NU PCF-CTU	For long term, samples will be stored at -80°C
Analysis center	[name] Lab	Samples will be stored for future analysis at Northwestern University.	[name] Lab
Assay methodology	IHC  Note: Tissue for IHC will be second priority.	Sequencing	Cytokine Panel

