**1.7 Rationale for Exploratory Studies**

Our preclinical data showed that EphB4 inhibition by sEphB4-MSA profoundly inhibited tumor growth in mouse model of Myc over expression and PTEN loss. In addition, we have also found that sEphB4-MSA induces T-Cell infiltration and expression of PD-L1 in tumors suggesting a role for immune cell mediated tumor regression. From this evidence, we would like to explore the effect of sEphB4-HSA in advanced prostate cancer patients as a single treatment or in combination with other agents. The rationale for obtaining archival pathologic specimen and peripheral blood to assess molecular features of the patient's disease is to gather correlative data that provides insight into the activity of sEphB4-HSA in this setting if response is seen. Results of this study will provide foundational data to further explore sEphB4-HSA therapeutic potential in other clinical settings of advanced prostate cancer as single agent and in combination with other agents, e.g. if immune cell infiltration associated with PD-L1 is seen, this can provide a rationale for combination with immune checkpoint therapy.

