8. Permission to obtain archival tissue samples of primary lesion and metastatic lesion sites will be obtained at baseline. The samples themselves will be collected only if available and only when requested by the Principal Investigator or Principal Investigator's designee; they may be collected at any time during the study, per PI request. Refer to the lab manual for details.
9. If there is concern about transformation to small cell cancer histology then a standard of care biopsy may be appropriate given that this is an exclusion criteria for this trial.
10. If tumor tissue is biopsied or resected as part of standard medical care or assessment from the time of study enrollment until progression then archival tissue from this biopsy/resection may be used for assay of the markers defined within the protocol to document molecular pathway characteristics and immune cell infiltration at that point to correlate with whether the cancer is responding, stable or progressing.
11. Patients will receive sEphB4-HSA 1000mg IV (60min infusion) on day 1 of each cycle along with continuation of androgen deprivation therapy. Refer to Table 4-2-1 for required premedication regimens.
12. Imaging must be completed and reviewed within 6 days (whenever feasible) prior to receiving treatment.
13. **Please see Table Below.** Beginning at Cycle 7, cycle length will be 21 days and patients will return for treatment on Day 1 of each cycle.
14. Patients will return for an End of Treatment (EOT) visit 30 ( $\pm 3$ ) days of the last dose of study treatment or prior to start of new treatment.
15. If off treatment for reasons other than disease progression, patients will be followed every 6 months, until objective progression or patient starts alternative therapy for a maximum of 1 year.
16. If patient has had molecular testing (i.e., NGS testing, genetic testing, genomic testing, etc.) performed as standard of care prior to study entry or at any time during study participation, collect a copy of the results report for correlative analyses. Refer to Section 9 for details.
17. Screening/baseline assessments are to be conducted within 1 month prior to registration unless otherwise indicated.

## Study Calendar Beginning at Cycle 7

Time Period	On Treatment (1 Cycle = 21 Days)						Off Treatment	
	Cycle 7	Cycle 8	Cycle 9	Cycle 10	Cycle 11	Cycle 12+	End of Treatment 	Follow-up 
	Week 13 Day 1	Week 16 Day 1	Week 19 Day 1	Week 22 Day 1	Week 25 Day 1	Week 28 Day 1		

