#### **9.4 Assay Methodology**

##### **9.4.1 Immunohistochemistry:**

For metastatic and primary tumor samples we will follow the standard protocol for immunohistochemistry to perform qualitative and quantitative measurement of EphB4, EphrinB2, PI3K-AKT pathway, MYC, PTEN pathway, AR, and for markers of Tumor Infiltrating lymphocytes and endothelial cells For immune cell staining, the pathologist will assign scores of 0, 1+, 2+ or 3+ based on staining intensity and percent positive cells per unit area of section

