**10.2 Analysis of secondary and exploratory objectives**

To estimate the distributions of time to PSA progression and rPFS (defined in Section 6.3), we will use Kaplan Meier methods, and estimate the median with two-sided 90% CI.

The estimated overall response rate in patients with measurable disease (Section 6.1.1) will be reported with two-sided 90% exact binomial CI.

For each patient within the population evaluable for toxicity (Section 6.1.1), recorded AE data over time will consolidated as the maximum grade observed of each AE type. All reported AE types will be tabulated by maximum grade using frequencies and percentages. Data on type, timing, frequency and attribution of AEs will also be summarized.

To explore if PSA response is associated with expression of EphB4 and ephrinB2 in archival metastatic and primary tumor CRPC specimens, and/or with aberrations in the PI3K pathway, P53, MYC. Marker values will be summarized according to PSA response status. Summaries will be descriptive and graphical; hypothesis testing is not planned.

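### No rule says whose archival tissue is requested or when, and masked IHC reading is not stated, so the exploratory marker-by-PSA-response summary is open to outcome-informed selection and reading

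*Combined protocol and SAP*

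**What the plan says.** Section 5, footnote 8, separates permission from collection. On permission: "Permission to obtain archival tissue samples of primary lesion and metastatic lesion sites will be obtained at baseline". On collection: "The samples themselves will be collected only if available and only when requested by the Principal Investigator or Principal Investigator's designee", at any time during the study. The notes to the Cycle 7+ calendar repeat this. The Section 9 table marks the tissue as optional and gives its timing as "When requested by the Principal Investigator or Principal Investigator's designee; Samples may be collected at any time during the study per PI request".

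Section 9.2 is worded differently. It lists specimens to be collected from each patient and includes archival primary and metastatic tissue where available, with no mention of a request.

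Section 1.7 describes the aim of obtaining archival tissue and blood as to "gather correlative data that provides insight into the activity of sEphB4-HSA in this setting if response is seen". Section 1.7.1 similarly ties the correlation with response to drug activity being seen.

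Section 9.4.1 has a pathologist score immune-cell staining from 0 to 3+. For EphB4, ephrinB2, the PI3K-AKT and PTEN pathways, MYC and AR it foresees qualitative and quantitative measurement, without naming a reader, scale or cut-off. It says nothing about masking.

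Section 10.2 then plans the comparison: "Marker values will be summarized according to PSA response status". The summaries are descriptive and graphical, without hypothesis tests.

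**The concern.** Whoever requests tissue can already hold the patient's PSA course and, through footnote 16, a standard-of-care molecular report. If that knowledge shapes which patients are requested, the tissue subset is no longer a neutral sample of responders and non-responders. A reader who knows the response while grading a stain can introduce a second distortion.

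At stake is the biomarker signal. Section 9.1.1 treats AR as a candidate predictive marker, and Section 9.1.2 wants to predict clinical response from EphB4 and associated genes. With so few responders expected, a handful of selective requests or shifted readings could look like an association. Leaving out non-responders would also weaken the comparison group.

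**Working it through.** **1. The plan's own figure.** The plan gives no figure for the tissue analysis. Its only computed figure is the Simon minimax design (Section 10.1), which reproduces. P(X ≤ 1 | 15, 0.10) = 0.549. Average N = 15 + 10 × (1 − 0.549) = 19.51. Summing over first-stage counts of 2 or more, alpha = 0.033 and beta = 0.198. None of this depends on tissue.

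**2. Can the outcome be known at the time of request?** PSA is taken on Day 1 of odd cycles, then every cycle from Cycle 7. The first on-treatment value after dosing is at Cycle 3 Day 1 (Week 5). Section 6.1.5 requires confirmation at least 4 weeks later, so a confirmed response can be known from about Week 9 (Cycle 5 Day 1). Requests remain open after that.

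**3. Inputs for illustration.** 6 responders and 19 non-responders of 25 (6 is the success boundary in Section 10.1). Marker positivity is 66% in both groups (the EphB4 figure in Section 1.3), so the true odds ratio is 1. All request and misreading rates below are assumptions.

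**4. Selection by response alone.** Positivity stays 66% in each group and the odds ratio stays 1.00. Precision falls:
- Tissue from all: SE = sqrt(0.66 × 0.34 × (1/6 + 1/19)) = 0.222, or 22 points.
- Tissue from 6 responders and 6 of 19 non-responders: SE = sqrt(0.66 × 0.34 × (1/6 + 1/6)) = 0.273, or 27 points.
- Variance ratio = (1/6 + 1/6) / (1/6 + 1/19) = 1.52.

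The response rate within the tissue subset is also inflated: 6/(6 + 19f) rises from 24% to 30%, 39% or 56% when f = 75%, 50% or 25% of non-responders are requested. That matters only if someone reads response rates by marker from the subset; Section 10.2 plans the opposite direction.

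**5. Selection that also depends on marker status**, for example through a molecular report. All responders are requested; marker-positive non-responders are requested at s times the rate of marker-negative ones. Positivity among requested non-responders = 0.66s / (0.66s + 0.34).

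| s | Positivity, non-responders | Positivity, responders | Odds ratio |
|---|---|---|---|
| 1.00 | 66.0% | 66% | 1.00 |
| 0.75 | 59.3% | 66% | 1.33 |
| 0.50 | 49.3% | 66% | 2.00 |
| 0.25 | 32.7% | 66% | 4.00 |

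**6. Selection by clinical course.** Suppose half the non-responders progress fast and are 80% positive, and the rest are 52% positive (average 66%). Requesting only the fast progressors creates a false gap of 80 − 66 = 14 points, about half the 27-point SE in step 4.

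**7. Reading with response known.** If a fraction u of truly negative responder samples is scored up, responder positivity = 0.66 + 0.34u. For u = 10%, 20% and 30% this is 69.4%, 72.8% and 76.2%, with odds ratios of 1.17, 1.38 and 1.65.

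**The case against.** A reader might infer that tissue is taken only from patients the PI picks, after their PSA is known, and is read by an unmasked pathologist. The documents do not support this.

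- Footnote 8 permits requests for everyone, and requests before any on-treatment PSA. Availability limits collection as well as the request.
- Section 9.2 describes collection from each patient. Its weight is uncertain: it still gives Cycle 3 Day 1 for the cfDNA sample where the Section 9 table gives Cycle 5 Day 1, so it may not be fully updated.
- On masking the documents are silent. Open-label treatment does not show that a laboratory reader holds PSA data. Sample details are referred to a Lab Manual that is not available here, so slide coding cannot be ruled out.
- The 0 to 3+ score is stated for immune-cell staining, which the Section 10.2 comparison does not name. It cannot be assumed to apply to EphB4, ephrinB2, the PI3K pathway, P53 or MYC.
- Sections 1.7 and 1.7.1 can be read at trial level: study the markers if the drug works. They do not say that individuals are requested once they respond.
- The numerical gaps come from assumed rates, and the loss of precision in step 4 is not bias.

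All of this stands, and it limits the point to what the plan leaves open. It does not supply a selection rule or a masking statement, and it leaves Section 9.2 in conflict with footnote 8 and the table. The absence of a hypothesis test removes a p-value but not a selection effect.

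**Conclusion.** The point holds as an unclosed route to bias, not as a demonstrated bias. Footnote 8 and the Section 9 table leave whether and when to request tissue to the PI or designee; Section 9.2 says otherwise; and masked reading is not stated. No size can be given from the documents alone. Under the assumptions above, a null association can appear as an odds ratio of 1.33 to 4.00 through marker-dependent requests, or 1.17 to 1.65 through shifted readings. Requests driven by response alone cost precision only.

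The reach is narrow. Blood samples are mandatory at fixed times, and standard-of-care molecular reports are collected whenever they exist, so only the tissue IHC is exposed. That analysis is exploratory and descriptive. The primary endpoint, the stage-one decision and the safety analysis are untouched. Severity is low.

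**What to change.** - **Footnote 8 (both calendars) and the Section 9 table:** reconcile with Section 9.2. Request available archival tissue for every dosed patient who has given permission, at registration or Cycle 1, whatever the later PSA. If funds limit numbers, go in registration order. Staining may wait until activity is seen, provided that the choice of slides does not depend on individual outcomes.
- **Section 9.4.1:** score all IHC on coded slides, with the reader masked to PSA response and clinical course.
- **Section 10.2:** report, by PSA response status, how many patients had tissue requested, received and scored.

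The cost is protocol wording, slide coding, and modest retrieval effort for about 25 patients, some of whom would not otherwise have been requested. The table asks for up to 12 slides. Permission is already sought at baseline, so no new consent step is needed.
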